### **2.2 Secondary Objectives (or Aim)**

The secondary objectives are to:

- Compare Sleep Well! to enhanced usual care on objective and caregiver-reported child sleep over post-intervention and follow-up
- Explore the effects Sleep Well! on child behavior outcomes over post-intervention and follow-up.

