### **3.1.2 Study Treatment Phase (start of the study intervention)**

Sleep Well! is a brief, behavioral sleep intervention. The intervention was originally comprised of healthy sleep advice and tested in the context of a sleep health education campaign for impoverished children. Based on our preliminary research regarding the need for sleep intervention in primary care, we have expanded the intervention to more comprehensively address poor sleep health behaviors (e.g., use of electronics at bedtime; inconsistent and variable sleep schedules; lack of a bedtime routine) as well as insomnia (difficulty falling and staying asleep; the need for caregiver presence at bedtime) and insufficient sleep in toddlers and preschoolers who are living in disadvantaged contexts. Intervention components are based on effective pediatric behavioral sleep treatments.

Adaptations to the program content and delivery have been made based on preliminary results from our previous studies (IRB 18-015041; IRB 19-016482) with primary care providers in the target urban primary care context and caregivers of young children with sleep problems who are reflective of the target intervention population. For example, interventionists will use strategies to engage with and empower families, such as motivational interviewing and collaborative problem-solving. In-person session content will be reinforced via phone calls from interventionists. We will also send families intervention session appointment reminders and information about intervention content (e.g., reminders to follow a bedtime routine), using Twilio, which is integrated with REDCap. No PHI will be transmitted via text message, and families will be asked to contact the study team or interventionist by phone if they have any questions or concerns during the study assessments or intervention phase. Consistent with standards of clinical care for behavioral health services in the CHOP primary care network, progress notes for intervention-related patient contact (sessions; phone calls) will be documented in the electronic health record.

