- *Actigraphy:* Objective child sleep will be assessed using a Philips Respironics, Inc., Actiwatch Spectrum, which is a water-resistant accelerometer device. Consistent with guidelines for the reliable and valid use of actigraph devices in children, caregivers will be instructed to keep the actigraph on their child's wrist continuously for the 7-day period at baseline and the 7-day period at follow-up, with the exception of bath time or swimming, to ensure that at least 5 days of data (to account for 2 days of missing data) are obtained. Caregivers will be asked to press an event marker at lights-off and lights-on. Actigraph data show an 85.1-88.6% agreement with polysomnography, which is the gold standard for objectively assessing sleep. Actigraph data will be analyzed using Philips Actiwatch software and scored using guidelines for young children. Actigraphs will generate daily total estimates of child sleep onset, offset, and sleep time variability. If the participant loses an Actiwatch or has difficulties with the device, the study team may choose to have the family discontinue engagement with actigraphy for subsequent data collection time points. Families will be given three options to return the actigraph to the study team after each assessment: 1) the study team will provide families with a pre-paid UPS envelope, 2) the family can coordinate a time with the study team to drop off the actigraph, or 3) the family can schedule a pick-up time with a delivery/courier service.
- *Center for Epidemiological Studies Depression Scale-Revised (CES-D-R):* Caregivers will report on their own depressed mood using the 10-item CES-D-R short form. This indicator may be used as a control variable in study analyses. The CES-D-R has shown good reliability and validity in diverse adult samples. There will be an attention check item placed randomly within the questionnaire to increase reliability in participant responses.

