- (2) Effect sizes for the magnitude of group differences will be drawn from the mixed effects models. The effect size for the condition  $\times$  time interaction is equivalent to Cohen's d-statistic. For categorical outcomes, percent change in the odds for the condition  $\times$  time interactions are provided as a measure of effect size.

Secondary sleep outcomes for these analyses will be drawn from the caregiver-rated Brief Child Sleep Questionnaire (BCSQ) and actigraphy (objective sleep measurement) and will include:

- Child sleep problems (BCSQ)
- Child bedtime resistance (also called "bedtime difficulties" BCSQ)
- Child sleep onset latency (BCSQ)
- Child night awakenings (frequency and duration BCSQ)
- Child sleep quality (BCSQ)
- Child total (BCSQ) and nighttime sleep duration (BCSQ and sleep onset to offset for actigraphy)

To examine secondary child behavior outcomes, we will examine change by group over time from pre-intervention to follow-up, exactly as described for the sleep outcomes (see above).

Secondary behavior outcomes drawn from validated the following validated clinical measures include:

- Child externalizing problems composite T-score (Child Behavioral Checklist for ages 1.5-5 years)
- Child internalizing problems composite T-score (Child Behavioral Checklist for ages 1.5-5 years)

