#### 8.1.2 Blinding

Families and Sleep Well! interventionists will not be blinded to condition assignment. In addition, it is not possible for the Co-I [name] or the Study Coordinator to be

blinded to condition assignment. However, all other members of the study team involved in data collection will be blinded to intervention group assignment. Blinding will be maintained by keeping a separate, password-protected list in REDCap that lists subject ID and group assignment. This database will be accessible only to the Co-I ([name]) and the Study Coordinator.

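### The only actigraphic outcome in section 6.4 is a sleep period, which counts night waking as sleep and so cannot detect fewer or shorter wakings

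*Combined protocol and SAP*

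**What the plan says.** The secondary objective in section 2.2 is to "Compare Sleep Well! to enhanced usual care on objective and caregiver-reported child sleep over post-intervention and follow-up". Section 3.1.2 names, among the problems the intervention addresses, "insomnia (difficulty falling and staying asleep; the need for caregiver presence at bedtime".

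In the section 6.4 list of secondary sleep outcomes, actigraphy appears once, as "nighttime sleep duration (BCSQ and sleep onset to offset for actigraphy". Waking and latency come from the caregiver questionnaire alone: "Child night awakenings (frequency and duration BCSQ" and "Child sleep onset latency (BCSQ". The additional exploratory analyses in 6.4 add no actigraphic outcome.

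Section 5.3 describes continuous wear for 7 days, scoring with the device software under guidelines for young children, and agreement with polysomnography of 85.1-88.6%. It says "Actigraphs will generate daily total estimates of child sleep onset, offset, and sleep time variability" and "Caregivers will be asked to press an event marker at lights-off and lights-on". It names no scored sleep minutes, wake after sleep onset or latency. Section 8.1.2 states that "Families and Sleep Well! interventionists will not be blinded to condition assignment".

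Section 6.5 gives a medium effect (0.5 SD) in clinical units: about 10 minutes less latency, 30 to 40 minutes more sleep, and about one fewer awakening. It also says that the effect sizes are meant to power a later full-scale trial.

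**The concern.** The variable is called sleep duration, but by its definition it measures the length of the sleep period. A child who used to lie awake in the middle of the night and no longer does has the same value before and after, provided that onset and offset do not move. For staying asleep, the objective comparison promised in section 2.2 therefore has no outcome behind it. The evidence on waking would come wholly from caregivers who know whether they received the program.

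Two things are at stake. A difference in reported waking could not be checked against the device. And the objective effect size taken forward to plan the next trial would be too small as an estimate of the gain in actual sleep, to the extent that this gain comes from less waking.

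**Working it through.** **Step 1: the definition.** Write I for the actigraphic interval, W for minutes awake between onset and offset, and S for minutes asleep.

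- Onset = bedtime + latency
- I = offset − onset
- S = I − W

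W does not enter I, so a change in W alone leaves I unchanged. Latency does enter I, through onset.

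**Step 2: an illustrative night.** The values are invented to show the mechanics. In minutes: bedtime 0, latency 40, W = 60, offset 600.

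| Change | I | S |
|---|---|---|
| None | 600 − 40 = 560 | 560 − 60 = 500 |
| Waking cut by 30 | 560 | 530 |
| Latency cut by 10, same bedtime and offset | 570 | 510 |
| Latency cut by 10, offset also 10 earlier | 560 | 500 |
| Bedtime 30 earlier, same latency | 590 | 530 |

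Row 2 is the gap: 30 minutes more sleep and no change in the outcome. Rows 3 to 5 show that I does respond to earlier onset, but cannot tell a shorter latency from an earlier bedtime.

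**Step 3: the plan's own figure (section 6.5).** The attrition step reproduces: 68/(1 − 0.15) = 80. The power step needs inputs that are not stated. I assume two-sided alpha of 0.05 and 34 per arm, with power ≈ Φ[d/√(1 − R²) × √(34/2) − 1.96].

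- R² = 0, d = 0.5: 0.5 × 4.123 − 1.96 = 0.10, power 54%.
- Power of 80% requires covariates to explain about 46% of the variance. I use R² = 0.46 below only so that d = 0.5 matches the plan's benchmark.

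**Step 4: what the interval would show.** The documents do not say how a gain in sleep divides between less waking and a longer period, so the share is shown over its full range. Visible d = 0.5 × (1 − share), taking the SD of the interval to equal that of sleep minutes (assumption).

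| Share of gain from less waking | Visible d | Power, R² = 0.46 | Power, unadjusted |
|---|---|---|---|
| 0% | 0.50 | 80% | 54% |
| 25% | 0.375 | 56% | 34% |
| 50% | 0.25 | 29% | 18% |
| 75% | 0.125 | 10% | 7% |
| 100% | 0 | none beyond type I error | none beyond type I error |

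**Step 5: latency.** The duration effect in 6.5 implies an SD of 30/0.5 = 60 to 40/0.5 = 80 minutes. A 10-minute shorter latency with bedtime and wake time unchanged lengthens I by 10 minutes, so d = 10/80 = 0.125 to 10/60 = 0.167, with power of 10-15% at R² = 0.46. It is diluted, but still visible.

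**The case against.** The strongest defense is that the plan states its operational definition openly, that onset and offset may be scored more reliably than brief waking in young children, and that this is one secondary outcome in a pilot whose primary endpoints are feasibility and acceptability. An objective comparison of sleep is made; it just does not cover every aspect of sleep. All of this stands. It bears on how serious the point is, and does not change what the interval measures.

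Three stronger readings are tempting, and the documents support none of them.

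- A reader might infer that the outcome is also blind to latency. It is not: with bedtime and wake time unchanged, shorter latency lengthens the interval minute for minute. What it cannot do is separate latency from a change of bedtime.
- A reader might infer that any real benefit could be supported only by unblinded report. Section 3.1.2 also targets inconsistent schedules, the absence of a bedtime routine and insufficient sleep. Earlier onset or a longer sleep period would show. Only benefit that comes through less waking is missed.
- A reader might size the loss by assuming 10-20 minutes per awakening and dividing by the 30-40 minute target: 10/40 = 25% to 20/30 = 67%. Section 6.5 gives no length for an awakening. It lists awakenings and duration as separate outcomes, and it does not say whether the duration figure is net of waking. The hidden share could be anything from 0% to 100%.

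It is also fair to say that latency measured from the event marker would not be fully objective, because the unblinded caregiver presses it.

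**Conclusion.** The point holds in a limited form. From its definition alone, the single actigraphic outcome listed in section 6.4 cannot detect fewer or shorter night wakings. That target, for which section 6.5 names about one fewer awakening as a relevant effect, is left to unblinded caregiver report. Section 5.3 also mentions sleep time variability, but 6.4 does not list it as an outcome, and it is not a measure of waking.

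An objective effect size carried forward would understate any gain that comes from less waking. The amount cannot be derived from the documents: the visible effect lies between d = 0.5 and d = 0 according to an unknown split. The power figures rest further on an assumed alpha, equal arms, equal SDs and an R² chosen to match the plan's 80%. This is a low-cost improvement to a secondary analysis and no threat to the primary endpoints.

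**What to change.** In section 6.4, keep the onset-to-offset variable but label it actigraphic sleep period. Add two supportive secondary outcomes from the same recordings: scored sleep minutes within that period, and wake after sleep onset. Name both in the section 5.3 list of variables generated. Latency from the lights-off marker to actigraphic onset may be added as exploratory, with a note that its start point is caregiver-marked. If the team prefers not to add these outcomes, the plan should say why, and should state that night waking has no objective measure.

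The cost is small. Continuous wear, the event marker and software scoring are already planned, so families do nothing more. The downsides are a few more outcomes in an already long secondary list, and wake scoring in young children that is likely to be noisier than onset and offset (the documents give no figure for this). That is why the additions should be labeled supportive.

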#### Additional exploratory analyses

Using the above growth model methods for secondary child sleep and behavior outcomes, we will also explore change in other sleep outcomes (BCSQ), including child bedtime routine consistency and sleep health behaviors (caffeine, fussy morning mood, bedtime fears, insufficient sleep) on the BCSQ and caregiver mood (CES-D) and sleep (PROMIS).

Exploratory analyses included tests of moderating effects for age of the child, whether the caregiver reported shift work, pretest measure of parent mood (CES-D), and pretest measure

of parent sleep (PROMIS). Moderation models will be run separately for each moderator and include main effects of the moderator and all higher order interaction terms with condition, time, and condition  $\times$  time.

## 6.5 Sample Size and Power

As is appropriate for a pilot study, the primary goal of this study to estimate effect sizes to fully power a future large-scale randomized controlled trial of the adapted behavioral sleep intervention through a subsequent R01 submission. However, we will have adequate power to detect the expected medium effects (found in similar efficacy and effectiveness trials for sleep) between groups on sleep outcomes. Based on previous primary care behavioral intervention research studies conducted at CHOP, we expect an approximate attrition rate of 15% at follow-up. A final sample size of 68 participants yields  $>80\%$  power to detect medium (0.5 SD) between-group effects using linear regression and adjusting for covariates (pre-intervention scores; socio-demographic variables) to evaluate change in sleep outcomes. The proposed sample of 80 dyads is thus sufficient for detecting medium intervention effects and accounts for potential attrition. Medium effects for relevant child sleep outcomes are equivalent to a  $\sim$ 10-minute reduction in sleep onset latency, a 30 to 40-minute increase in sleep duration, and a reduction of  $\sim$ 1 night awakening—all clinically meaningful results.

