### 5.3 Demographic and Parent and Child Behavior Measures (Secondary Outcomes and Covariates)

- *Child Demographic Information:* Child demographic information will be abstracted from the EMR (see section 5.1.1).
- *Caregiver Demographic and Family Questionnaire:* Caregivers will complete a caregiver and family demographic questionnaire at baseline. Child data will include CHOP primary care site where child receives care, whether the child attends daycare/preschool, and where the child typically sleeps. Caregiver/family data will include age, sex, race, ethnicity, highest educational level obtained, relationship to child, income, employment status, relationship status, number of times the family has moved in the last year, and information about children and adults living in the home.
- *Previous Service Use Form:* At each assessment, caregivers will complete a form related to any previous treatment for child sleep or behavior problems.
- *Brief Child Sleep Questionnaire (BCSQ):* Caregivers will complete the BCSQ to report on child sleep habits (sleep time, total sleep durations, night wakings, aspects

of the sleep environment, etc.) and the severity of any caregiver-perceived sleep problems. The BCSQ is appropriate for children ages 1-5 years and has shown good reliability and moderate correspondence with actigraphic recordings of child-sleep. There will be an attention check item placed randomly within the questionnaire, which is designed to detect individuals who are quickly responding to survey questions without sufficient attention to item content. Previous research has demonstrated that the inclusion of an attention check item can increase questionnaire reliability.

- *7-Day Daily Child Sleep Diary:* Items drawn from the BCSQ will be used to track regularity in child bedtime routines, bedtime activities, and 24-hour sleep schedule over 7 days at baseline (pre-intervention) and follow-up (post-intervention).

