For qualitative interview data, transcribed interviews will be coded by study team members using an iterative process that begins with open coding, codebook development and refinement, and consensus regarding the codes. We will use an integrated approach, with a priori codes based on prior work and themes emerging from the data. Once a stable codebook is developed, approximately 20% of the data will be double coded for reliability purposes (weighted kappa). Separate codebooks may be developed for the Sleep Well! participant interviews and for the enhanced usual care condition interviews. We will also explore how themes from the intervention group vary by quantitative caregiver-reported outcome data (e.g., sleep problem perception) and family factors (e.g., shiftwork). We will also examine variation using this method for the usual care group interviews.

Data analysis for the secondary sleep outcomes (below) will include (1) the application of mixed effects growth models, and (2) generating effect sizes, as follows.

- (1) Mixed effects linear growth models will also be applied to compare overall change in continuous outcomes between groups from pre-intervention to follow-up using an intent to treat approach with maximum likelihood estimation. Individual variability in the outcomes from pre-intervention through the follow-up assessments will be predicted by a two-level fixed effect condition variable (coded 0 for enhanced usual

care and 1 for intervention), a time variable with the intercept defined as the pre-intervention assessment and weeks between this assessment and last follow-up, and the group  $\times$  time interaction. Models will account for random effects (intercept, time) and fixed effects (group, and time by group). The time by intervention group interaction identifies whether there is a significant between-group difference in change since pre-intervention. Categorical outcomes will be modeled as mixed-effects growth models with maximum likelihood and a logit link. Model parameters include those described for the continuous models and a threshold parameter at each timepoint. Any sleep and behavior outcomes that are significantly different by group at pre-intervention will be included as covariates in all models.

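### The over-80% power in Section 6.5 for a 0.5 SD sleep effect does not follow from its stated inputs, and it is computed for a different analysis from the group-by-time test planned in Section 6.4

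*Combined protocol and SAP*

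**What the plan says.** Section 6.5 calls the study a pilot whose main goal is to estimate effect sizes for a later trial. It then adds: "However, we will have adequate power to detect the expected medium effects". With 15% attrition, 68 dyads are expected to remain, and these are said to give more than 80% power "to detect medium (0.5 SD) between-group effects using linear regression and adjusting for covariates (pre-intervention scores; socio-demographic variables) to evaluate change in sleep outcomes". It concludes: "The proposed sample of 80 dyads is thus sufficient for detecting medium intervention effects and accounts for potential attrition".

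Section 6.4 plans a different analysis of the sleep outcomes: a mixed effects linear growth model from pre-intervention to follow-up. "Models will account for random effects (intercept, time) and fixed effects (group, and time by group"). The test is the interaction: "The time by intervention group interaction identifies whether there is a significant between-group difference in change since pre-intervention". The pre-intervention score is the first time point of the outcome. The only covariate rule is: "Any sleep and behavior outcomes that are significantly different by group at pre-intervention will be included as covariates in all models".

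Section 5.3 only hints at further adjustment. Its heading reads "Demographic and Parent and Child Behavior Measures (Secondary Outcomes and Covariates"), and of the caregiver depression score it says: "This indicator may be used as a control variable in study analyses". No section commits a socio-demographic term to the model.

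**The concern.** Two things do not fit. First, 68 children and 0.5 SD do not by themselves give more than 80% power. The gap must be closed by variance that the covariates explain, and no value for that is given. Second, the power refers to a regression adjusted for baseline and socio-demographic variables, whereas the planned test is an interaction in a growth model that treats baseline as an outcome.

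What is at stake is interpretation. A reader told that power is adequate could take a non-significant sleep result as evidence against a medium effect, when the interval may be nearly as wide on each side as the effect itself. Section 6.5 also makes effect-size estimation the main goal but states no expected precision.

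**Working it through.** **Inputs from the documents.** Section 6.5: 80 enrolled, 15% attrition, 68 completers, effect 0.5 SD. Sections 3.1 and 3.1.4: post-intervention at weeks 9–16 and follow-up at weeks 15–24.

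**Assumed, because not stated.** 1:1 allocation (34 per arm, the most favourable ratio); two-sided 0.05 unless noted; 0.5 measured on the raw outcome SD; the correlations r used below.

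**Attrition.** 80 × 0.85 = 68, which agrees with the plan.

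**Regression as described in 6.5, one post-baseline value.** With n = 68 and residual variance 1 − r², the noncentrality is 0.5/√(1 − r²) × √(68/4), where √17 = 4.123. Power comes from the noncentral t (66 df unadjusted, 65 df with one covariate).

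| r | Noncentrality | Two-sided 0.05 | One-sided 0.05 |
|---|---|---|---|
| 0 (no gain) | 2.062 | 52.9% | 65.4% |
| 0.5 | 2.380 | 65.0% | 76.1% |
| 0.6 | 2.577 | 71.9% | 81.7% |
| 0.7 | 2.887 | 81.2% | 88.7% |

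Solving for 80% gives R² = 0.474 two-sided (r about 0.69) and 0.327 one-sided (r about 0.57). Using five covariates instead of one moves power by about 0.1 percentage point. If 0.5 were meant in residual SD units, covariates would add nothing and power would stay near 53%.

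**Group-by-time test as planned in 6.4.** Take a continuous outcome, three balanced visits, constant between-visit correlation r and a true difference growing linearly to 0.5 SD at follow-up. The interaction test is then a t-test on per-child least-squares slopes (66 df). With time scaled so that follow-up = 1, the slope variance per child is (1 − r)/SS + s. SS is the sum of squares of time about its mean, and s is the random-slope variance in SD² at follow-up. The standard error of the group difference is √(2/34 × that variance).

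- Weeks 0, 9, 15: SS = 0.507. Weeks 0, 16, 24: SS = 0.519.
- Example, r = 0.5, s = 0, weeks 0/9/15: variance 0.5/0.507 = 0.987; SE = 0.241; noncentrality 0.5/0.241 = 2.075; power 53.4%; 95% CI half-width 1.997 × 0.241 = 0.48 SD.

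| r | Power, s = 0 | Power, s = 0.1 (illustrative) | 95% CI half-width, s = 0 |
|---|---|---|---|
| 0.5 | 53–54% | about 50% | 0.48 SD |
| 0.6 | 63–64% | 58–59% | 0.43 SD |
| 0.7 | 75–76% | 69% | 0.37 SD |

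The ranges span the two visit schedules. With s = 0, 80% power needs r of about 0.73.

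**Regression half-width, for comparison.** 1.997 × √(2/34) = 0.48 SD unadjusted; multiplied by √0.75 this is 0.42 SD at r = 0.5.

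**The case against.** **Covariates are part of the claim.** This is fair: 6.5 specifies adjustment, so 53% is a floor and not the expected power. A reader might infer that the trial really has 53% power, or that more than 80% is out of reach. The documents support neither, since a correlation near 0.7 would deliver it. What stands is that no such value is stated or sourced.

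**An arithmetic slip might be inferred.** N = 68 is exactly the smallest sample giving 80% power for a joint test of two predictors at f² = 0.15. On a single group term that f² corresponds to 2√0.15 = 0.77 SD rather than 0.5. The documents do not say that this was the calculation, so it shows no error. The one calculation that 6.5 sets out, the attrition step, is correct.

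**More data may be available.** The Abstract allows up to 100 dyads. At 15% attrition that leaves 85, giving 62% unadjusted, 75% at r = 0.5 and 81% at r = 0.6 in the regression; but 6.5 rests its claim on 80 and 68. Maximum likelihood also keeps partial records: if the 12 lost dyads miss only follow-up, the growth-model figures rise to about 56–58%, 66–67% and 78–79%. Section 3.1 adds a mid-point sleep assessment for the intervention arm only, and 6.4 does not say whether it enters the model. If it does (assumed at week 3 on the shorter schedule and week 5 on the longer, zero slope variance, 68 completers), the figures are again about 56–58%, 66–67% and 78–79%. These gains are modest.

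**It is a pilot.** Sections 6.1 and 6.4 make feasibility and acceptability primary and descriptive, and no decision rule uses the power figure. That limits the consequence. It does not justify the statement that power is adequate, which 6.5 chose to make.

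**Conclusion.** The point holds as an unsupported power claim and a mismatch between 6.4 and 6.5. It is not a demonstrated arithmetic error. Under the stated assumptions, the regression in 6.5 has 65–81% power for correlations of 0.5–0.7 (53% with no covariate gain) and passes 80% only if covariates explain about 47% of outcome variance, or about 33% one-sided. The test planned in 6.4 has about 53–76% over the same correlations with zero slope variance and about 50–69% with the illustrative slope variance.

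The mismatch between sections stands whatever correlation is assumed. The growth-model figures apply to continuous outcomes and balanced visits; the outcomes that 6.4 models with a logit link are not covered. A reader might also infer that the sample must grow or that the trial's conclusions are compromised. Neither follows, because sleep outcomes are secondary and the primary endpoints are descriptive. The change should be made, but it alters no primary conclusion.

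**What to change.** Keep 80 dyads and make the two sections describe one analysis.

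- **Option A, 6.4 unchanged.** In 6.5, compute power for the group-by-time test. State alpha, sidedness, allocation, between-visit correlation and slope variance, with sources, and say whether the mid-point sleep questionnaire, which Section 3.1 assigns to the intervention arm only, enters the model.
- **Option B.** In 6.4, name the baseline-adjusted regression and its full covariate list as the planned test. In 6.5, give alpha, sidedness, allocation and a sourced R².

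Unless a sourced correlation or R² supports them for the chosen test, replace the over-80% figure and the statements of adequacy and sufficiency with that test's range and expected 95% CI half-width. Under the assumptions above:

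- **For A:** about 53–54%, 63–64% and 75–76% at correlations of 0.5, 0.6 and 0.7, with half-widths of about 0.48, 0.43 and 0.37 SD, noting that slope variance lowers power and widens the interval.
- **For B:** 53% without covariate gain, 65% at 0.5 and 81% at 0.7, with half-widths of 0.48 SD unadjusted and 0.42 SD at 0.5.

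Say that these figures cover continuous outcomes only, and report group comparisons as estimates with 95% confidence intervals.

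Cost: one calculation and one rewritten paragraph, plus a covariate list in 6.4 under option B. No extra participants are needed. The stated power will probably look less favourable.
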